1.2 SCHEMA

1.3 SCHEDULE OF ACTIVITIES (SOA)

Study Visit	Screening/ Baseline	Visit 1	Visit 2	Visit 3	Visit 4	Visit 5	Visit 6	Visit 7	Visit 8	Visit 9	Visit 10	Visit 11	Visit 12/EOS	Follow Up
Study Week ¹	0	4	8	12	16	20	24	28	32	36	40	44	48	52
Location	Clinic	Phone	Phone	Clinic	Phone	Phone	Clinic	Phone	Phone	Clinic	Phone	Phone	Clinic	Phone
Informed Consent	X													
Enrollment to MiAsthma Registry	X													
Inclusion/Exclusion Review	X													
Demographics	X													
Smoking/Tobacco Use History	X													
Medical History- General/Asthma	X													
Conmeds- General/Asthma	X	X	X	X	X	X	X	X	X	X	X	X	X	X
Exacerbations/Healthcare Utilization	X	X	X	X	X	X	X	X	X	X	X	X	X	
Patient Reported Outcomes (PRO) ²	X			X			X			X			X	
FeNO (Clinical) ³	X			X			X			X			X	
CBC w. Differential (Clinical) ³	X			X			X			X			X	
Immunoglobulin (IgE) (Clinical) ³	X			X			X			X			X	
Inhaler Teaching	X													
Dispense Digihaler™	X	X	X	X	X	X	X	X	X	X	X	X	X	
Registration/Onboarding App	X													
Home Spirometry Teaching	X													
Dispense Home Spirometer	X													
Adverse Events	X	X	X	X	X	X	X	X	X	X	X	X	X	X
Subject Fee/Stipend	X			X			X			X			X	
Phone Call		X	X		X	X		X	X		X	X		X
Ship Drug (As Needed)		X	X		X	X		X	X		X	X		
1 Study visits have a ± 7 Day window. 2 Patient Reported Outcomes include the Asthma Control Test (ACT), AIRQ, and the St. George’s Respiratory Questionnaire 3 Clinical activities will be captured if they are available but will not be done specifically for the study.														

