1 PROTOCOL SUMMARY

1.1 SYNOPSIS

Title: Utilizing Advances in Digital Inhaler Technology to Understand Heterogeneous Treatment Responses to Biologics in Severe Asthma

Study Description: This real-world study aims to determine baseline inhalation parameters and patterns of use in patients receiving treatment with TEVA digital inhalers, and to develop predictive models for asthma exacerbations and response to biologics using data collected from these devices.

Objectives:

Primary Objective:
To determine the baseline inhalation parameters and patterns of use of both the maintenance (AirDuo®) Digihaler™ and rescue (ProAir®) Digihaler™ in patients with severe persistent asthma who are being treated with biologics.

Secondary Objectives:

1. To determine the predictive value of inhalation parameters, including peak inspiratory flow (PIF), inspiratory time and volume, and number of inhaled doses on asthma exacerbations in a population of severe asthma patients on biologics.
2. To determine whether inhalation measurements can serve as surrogates of standard expiratory flow measurements. Specifically, to determine the correlation between PIF with FEV1 and identify thresholds for changes in PIF that are associated with a clinically meaningful increases or decreases (10%) in lung function as measured by conventional spirometry (e.g., FEV1).
3. To determine the impact of variable degrees of adherence to maintenance therapy on outcomes to biologics. The Digihaler™ will allow us to collect accurate information on adherence that will be utilized to divide patients into groups and to assess asthma outcomes such as change in mean FEV1, exacerbations, oral steroid reduction, and asthma control (using the asthma control test scores over time) in patients receiving biologic therapies.
4. To determine the impact on inhalation parameters on categorical response to biologics. Response will be categorized as non-response, partial and complete response on the basis of six factors: a 50% reduction in exacerbations, any reduction in maintenance OCS dose, change of at least 10% in FEV1, improvement of 3 points in ACT score, and patient perception of global improvement in asthma.

Exploratory Objectives

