5. To evaluate the asthma control and health care utilization of subjects as measured by the number of exacerbations (acute worsening of asthma requiring at least 3 days of corticosteroids or a doubling dose of maintenance steroids), Emergency and hospitalization encounters, and patient-reported perceptions of asthma control.
6. To employ machine learning techniques to a robust well characterized cohort with clinical, biological, and digital markers to develop a predictive algorithm aimed at identifying responders to biologics. In addition, we would aim to develop an algorithm that can detect early changes in measured parameters that can predict long-term improvements in asthma control and exacerbations when biologics are initiated. The latter objective will be achieved by focusing on the subgroup of patients initiating biologics for the first time or switching between biologics due to perceived inadequate response.

Endpoints:

Primary Endpoint:

Mean and median number of (daily) doses of ProAir® Digihaler™ and AirDuo® Digihaler™ utilized at baseline, temporal patterns in rescue and controller medication utilization, and within-patient parameter mean, median, and variance per-inhalation to establish baselines.

Secondary Endpoints:

1. Proportion of patients with different rates of adherence.
2. Proportion of Patients achieving non-response, partial-responses, and complete response to biologics.
3. Change in Main Peak Inspiratory volume from baseline up to one year.
4. Change in Mean Inspiratory Time from baseline up to one year.
5. Change in mean peak inspiratory flow (PIF) from baseline up to one year.
6. Change in mean forced expiratory volume in one second (FEV1) from baseline up to one year.

Exploratory Endpoints

7. Number of exacerbations from baseline up to one year.
8. Number of hospitalizations.

9. Number of emergency room visits.
10. Mean Asthma Control Test (ACT) scores.
11. Algorithm that produces a daily asthma exacerbation probability given a set of baseline and current inhalation parameters. A confusion matrix summarizing the algorithm's performance on training dataset and from which performance statistics (accuracy, sensitivity, specificity, etc.) can be computed.

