
test scores over time) in patients receiving biologic therapies.
 
Definitions: Adherence rates will be defined as: high (>80% of puffs), moderate (50-80% of puffs) and low levels (<50% of puffs) of adherence to maintenance inhalers (assuming an expected baseline usage of two puffs per day).
		
non-adherence to inhaled therapies and lead to incorrect conclusion that the biologic is not effective. In addition, little is known about how patients with severe asthma utilize their inhalers once biologics are initiated and more importantly if it is safe to discontinue these therapies altogether.

To determine the impact on inhalation parameters on categorical response to biologics. Response will be categorized as non-response, partial and complete response on the basis of six factors: a 50% reduction in exacerbations, any reduction in maintenance OCS dose, change of at least 10% in FEV1, improvement of 3 points in ACT score and patient perception of global improvement in asthma.
	
 • Proportion of patients achieving non-response, partial and complete response to biologics. 
Tests: Summary, chi-squared test, and Tukey’s HSD test statistics of inhalation parameters by response group.
	
Response to biologics is heterogeneous, and it is unclear if inhalational parameters measured by the Digihaler™ are correlated with degree of response.

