8.1.1.2 IN PERSON/CLINICAL VISITS (V3, V6, V9, V12)

Patients will return to clinic every three months to check in with the study team and to provide additional inhalers for the study. During the in-person visits the following events will take place:

- Review of Current Medications
- Review of Asthma Exacerbations and Healthcare Utilization
- Collection of Clinical Variables (*if available*) including FeNO, CBC w. Differential, and Immunoglobulin E (IgE) Levels
- Dispensation of Inhaler
- Adverse Event Assessment
- Collection of Patient Reported Outcomes

- Asthma Control Test (ACT), AIR-Q, SGRQ
- Device Re-Education (As Needed)

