8.1.1.3 INTERIM PHONE CONTACT (V1, V2, V4, V5, V7, V8, V10, V11)

Patients will be contacted monthly between in person visits to assess the following:

- Review of Current Medications
- Review of Asthma Exacerbations and Healthcare Utilization
- Shipping of Inhaler (As Needed)
- Adverse Event Assessment
- Device Re-Education (As Needed)

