3. Patients will be assigned to one of three adherence groups (low, moderate, high) based on Digihaler™ inhalation usage parameters over the previous month. We will use the Chi-squared test to determine if group differences exist for each asthma outcome over the next month, and Tukey's Honest Significant Difference test to determine which groups are significantly different.

4. Patients will be assigned to one of three biologics response groups (non, partial, complete) based on six asthma factors (described earlier). We will use the Chi-squared test to determine if group differences exist for each inhalation parameter, and Tukey's Honest Significant Difference test to determine which groups are significantly different.

5. To develop an algorithm that can predict patients that will respond to biologics regression or classification models. Since we expect our training set to be relatively small with a low event rate, we plan to use the entire inhalation parameter dataset for model training but will employ repeated k-fold cross-validation to reduce variance (over-fitting) and include non-linear features to reduce bias (under-fitting). We do not know a priori whether regression or classification would be the appropriate approach to this question so we will test models using both approaches. The classification approach can be formulated as either a two-class problem – Non vs. Partial or Complete responders, or Non or Partial vs. Complete responders – or a three-class problem – Non vs. Partial vs. Complete. The regression approach requires a two-class formulation using logistic regression. Different models will be fit for different formulations and the performance of each model assessed and compared to others.

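### One listed response factor, the patient's own view of overall improvement, has no planned source of data, so the biologic response groups cannot be scored consistently as defined

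*Combined protocol and SAP*

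**What the plan says.** Section 1.1, secondary objective 4, sets the rule: "Response will be categorized as non-response, partial and complete response on the basis of six factors". The list that follows ends with "improvement of 3 points in ACT score, and patient perception of global improvement in asthma". The objectives table in section 3 repeats it in the secondary row on categorical response ("improvement of 3 points in ACT score and patient perception of global improvement in asthma") and again in an exploratory row.

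The resulting category is secondary endpoint 2: "Proportion of Patients achieving non-response, partial-responses, and complete response to biologics". Section 9.4.3 item 4 then forms the comparison groups and adds no further definition: "Patients will be assigned to one of three biologics response groups (non, partial, complete) based on six asthma factors (described earlier"). Item 5 of the same section takes response as the outcome to be predicted.

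On data collection, footnote 2 to the schedule in section 1.3 says "Patient Reported Outcomes include the Asthma Control Test (ACT), AIRQ, and the St. George"'s questionnaire (SGRQ). The in-person visit list in 8.1.1.2 gives "Asthma Control Test (ACT), AIR-Q, SGRQ", and the baseline list in 8.1.1.1 gives the same three. Section 8.1.1.3 introduces the phone contacts with "Patients will be contacted monthly between in person visits to assess the following"; its list covers medications, exacerbations and utilization, shipping, adverse events and device re-education, and contains no patient-reported outcome.

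**The concern.** A response definition can only be applied if each component is measured. Here one component is a judgement that only the patient can give, and the schedule contains no question that asks for it.

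The response category is a secondary endpoint, the grouping variable for the comparison of inhalation parameters, and the label on which the responder model is trained. If one component has no planned source, whoever builds the analysis dataset must choose between reading it out of clinic notes where they exist, treating it as not met, and leaving it out. Each choice can move patients between categories, and the plan does not say which applies. Section 9.4.1 joins the inhaler, record and questionnaire data only after data collection ends. By then a patient's perception at a given visit cannot be reliably recovered, and the choice would be made with the data in view.

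**Working it through.** The plan states no figure on this point, so there is none to reproduce. The check sets each listed factor against the places where the plan says data are collected.

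**Count of factors.** Stated: 6. Listed: 5. Difference: 6 − 5 = 1 factor not identified anywhere.

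**Source for each listed factor.**

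1. 50% reduction in exacerbations: schedule row for exacerbations and healthcare utilization (1.3); definition in 8.1.2.3. Source named.
2. Any reduction in maintenance oral steroid dose: concomitant medication row (1.3), with dose and dates recorded under 6.5.1. Source named.
3. At least 10% change in FEV1: home spirometry (8.1.2.5). Source named.
4. 3-point ACT improvement: patient-reported outcome row (1.3); instrument in 8.1.2.6. Source named.
5. Patient's perception of overall improvement: no schedule row, question, scale, visit, reference period or cut-off. No source named.

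So 4 of the 5 listed factors have a named source and 1 does not.

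**Visits.** The schedule has 14 contacts: 5 in clinic (weeks 0, 12, 24, 36, 48) and 9 by phone (V1, V2, V4, V5, V7, V8, V10, V11 and the week 52 follow-up). Patient-reported outcomes are marked at the 5 clinic visits only, with the same 3 instruments each time.

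**Could one of the three instruments be the factor?** Section 8.1.2.6 describes them as follows.

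- ACT covers symptoms and short-acting bronchodilator use. A 3-point change on it is already factor 4, so factor 5 must mean something else or ACT would count twice.
- AIRQ yields a score for level of control, not a rating of change.
- SGRQ yields a 0 to 100 score in which higher means more limitation. It touches on perceived well-being, but no section links it to the response rule or sets a change that would count as improvement.

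**Could another route supply it?**

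- The registry (8.1.2.1) takes in patient-reported outcomes assessed in clinic, without naming them.
- Section 4.2 draws clinical data from the electronic record.
- Section 5.5 asks providers in other clinics to document response to the biologic. That is provider documentation, and it covers only patients recruited from those clinics.
- The app (8.1.2.4) takes daily self-assessments of respiratory symptoms.
- The questionnaire planned in 4.2 concerns opinions of the app.

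None of these names a patient rating of improvement or a time at which it is taken.

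**Why the handling matters.** Suppose, for illustration only, that complete response means meeting every factor that is counted. A patient who meets all four collectible factors is a complete responder if factor 5 is left out (4 of 4), and not a complete responder if factor 5 is counted as not met (4 of 5). The data are identical and the group differs. The plan fixes neither the scoring rule nor the handling of an absent factor.

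**The case against.** The strongest reply is that not naming a source is not the same as having no data. Footnote 2 says the outcomes *include* the three instruments, which need not be exhaustive. The registry's list of patient-reported outcomes is open. Response is expected to be documented in routine care, at least in the other clinics. Section 10.1.9.1 promises a Manual of Operations with data-collection detail, which is not among the documents. SGRQ has a patient-perception element and is taken at baseline and four later visits. Section 3 also pairs patient perceptions of asthma control with mean ACT score in an exploratory row, so the authors do use questionnaire scores for perceptions.

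Part of this stands. A reader might infer that the factor will be missing for every patient, that a fixed share of the composite is lost, or that no patient can reach complete response. The documents do not support any of these. Incidental entries may exist. A share of the composite presumes equal weights and a known number of factors. The claim about complete response presumes that all factors are required and that an absent factor counts against the patient. The plan contains none of these rules.

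The rest does not remove the gap. The baseline list, the in-person list and section 8.1.2.6 give the same three instruments and no fourth. Routine-care entries would differ in wording, timing and availability between patients. Using an SGRQ change as the factor would be a new definition, and it would have to be written down with a threshold.

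It is also fair to say that this is not the only obstacle. With six factors stated, five listed and no count separating the three categories, the response rule could not be applied as written even if this item were collected.

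**Conclusion.** The concern holds in this form: a listed component of the response definition has no planned, systematic source, so secondary endpoint 2, analyses 4 and 5 in 9.4.3 and the responder model in the exploratory objectives cannot be scored consistently as defined. The extent is one of the five listed factors. The effect on response proportions cannot be calculated, because it depends on scoring and missing-data rules that the plan does not give.

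The primary descriptive endpoint does not use the response category and is unaffected. The other four listed factors have sources, so a reduced definition could be scored, but that would not be the definition written.

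The conclusion rests on reading the schedule, visit lists and section 8.1.2.6 as the full set of planned patient-reported outcomes. A Manual of Operations that added a specific improvement question at set visits would close the collection gap. It would leave the factor count and the scoring rule open unless it also settled those.

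**What to change.** Choose one of two routes before any response data are examined, which includes the initial analysis planned in 9.4.6.

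- **Collect it.** Add one patient global-rating-of-change question at V3, V6, V9 and V12, entered in the schedule (1.3), the in-person visit list (8.1.1.2) and the patient-reported outcome section (8.1.2.6). State the reference period and the answer that counts as improved. Section 5.1 admits both patients already on a biologic and patients about to start one, so say explicitly what those already treated at enrolment are comparing with.
- **Delete it.** Remove the factor from secondary objective 4 in 1.1 and from both rows of the section 3 table that carry it.

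With either route, reconcile the six factors stated with the five listed wherever the number appears (1.1, section 3, 9.4.3 item 4). State in 9.4.3 item 4 how many factors define non, partial and complete response. Adding or deleting the question alone would not make the category scorable.

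The first route costs one extra question at four existing visits, and patients enrolled before the change may lack early readings. The second is a wording change, at the price of losing the patient's overall judgement from the response definition.

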2 INTRODUCTION

2.1 STUDY RATIONALE & BACKGROUND

Severe asthma affects 10% of the adult population and these patients suffer an increased number of exacerbations and subsequent accelerated decline in lung function. Asthma exacerbations are poorly understood and the ability to predict exacerbations is limited. The factors associated with an increased risk of exacerbations include a prior history of exacerbations, elevated type 2 markers, lower lung function and increased short acting beta agonist (SABA) use. The ability to predict the onset of each isolated exacerbation event and to thus intervene is hampered by a lack of access to real-time information about both SABA use and lung function parameters. The Digihaler™ has demonstrated changes in both PIF and SABA doses surrounding acute asthma events (TEVA, unpublished data). The clinical utility of this information will be tested in future trials that aim to examine the impact of data from the Digihaler™ on clinical decision making. The data from the Digihaler™ coupled with clinical characteristics and biomarkers could be utilized to revolutionize how asthma is monitored and how exacerbations are detected.

Two-thirds of patients with severe asthma have evidence of type 2 inflammation that is targeted by five approved biologics for asthma. In clinical trials biologics have demonstrated significant impacts on exacerbation reduction, oral steroid sparing effects and improvements in quality of life. In all the clinical trials patients were required to remain on their maintenance inhaled (background) therapies and use of rescue bronchodilators was reported using patient self-report in symptom diaries. Little is known about how patients use their maintenance and rescue medications for asthma following the initiation of biologics and whether these patterns of use impact their response to these therapies. Furthermore, information about inhalation parameters such as peak inspiratory flow and inspiratory time and the importance of variability in these parameters that are measured in the Digihaler™ are lacking. The TEVA Digihaler™ offers an opportunity to obtain granular data about inhaler use in patients with severe asthma. Importantly, this data will be incorporated with clinical, biomarker, and digital data from the cohort, and machine learning methods will be utilized to determine if predictive algorithms can be developed to not only identify exacerbations but also provide a priori prediction of likelihood of response to biologics. These models will enhance our understanding of disease variability and characteristics, enable us to perform future trials testing the hypothesis that “baseline characteristics and early changes in lung function parameters and medication use will provide early and accurate predictions of future outcomes when biologics are initiated,” and could provide the basis for early discontinuation of ineffective therapies, saving money and time for patients who are currently subjected to long trials with biologics prior to switching or discontinuation.

Asthma is a highly prevalent disease that affects 30 million people in the United States. The vast majority of asthma patients are well controlled with conventional asthma therapies; however, 10% of patients have severe disease that is associated with significant comorbidity and exposure to high doses

of oral corticosteroids (OCS). This exposure to OCS increases the odds of developing co-morbid diseases such as diabetes, hypertension, cardiac disease and cataracts¹. Severe asthma is associated with an increased risk of acute events/exacerbations that result in accelerated lung function decline² and increased morbidity and mortality. Exacerbations are difficult to characterize and what is currently known about the changes in lung function prior to, during, and after exacerbations is predominantly focused on expiratory flow and highly reliant on patient diaries and peak flow meters. The variability in inspiratory flow parameters during acute events is not well characterized and may significantly impact inhaled drug delivery. The Digihaler™ data could enable the development of next-generation asthma action plans and novel real-time asthma control monitoring. Furthermore, this technology will allow the development of novel methods to monitor asthma and enable earlier detection of acute asthma exacerbations. The early detection of asthma attacks would enable clinicians and empower patients to intervene and perhaps change the trajectory of illness.

The rapid development of new biologics approved for the management of severe asthma with type II inflammation has led to a revolution in asthma care³⁻⁵. The term "type II inflammation" refers to an increase in the levels of type II cytokines including interleukin IL-4, IL-5 and IL-13, which results in downstream production of IgE and eosinophils. Sixty percent of severe asthma patients have evidence of type II inflammation^{6,7}. Surrogate biomarkers including peripheral eosinophils, fraction of exhaled nitric oxide (FeNO) and total IgE levels are used to phenotype patients with severe asthma and to guide biologic drug selection⁸. Eosinophils have been shown to predict response to IL5 and IL4 targeted therapies and FeNO is a predictor of response to anti-IL4 therapy^{9,10}.

The response to targeted biologic therapies is heterogeneous despite the use of biomarkers to select potential responders. Unfortunately, even when patients with a high likelihood of response are selected, 10-15% have complete non-response in all clinical parameters, 40% have a robust and complete response to therapy, and the remainder of patients have a partial response. This is likely related to the presence of overlapping inflammatory pathways, co-morbid eosinophilic diseases that affect response to therapy, possible sub-optimal dosing of drug, and the lack of highly specific biomarkers.

Little is known about how biologics impact the use of inhaled asthma therapies and whether the heterogeneity in responses to biologics could be partially attributed to nonadherence with maintenance therapies once biologic therapy is initiated. Data collection on use of both maintenance and inhaled therapies is based primarily on patient self-reporting. The Digihaler™ presents a unique opportunity to gain invaluable insights into both patterns of use of inhaled therapies and changes in inspiratory flow parameters in patients with severe asthma who are treated with biologics. In addition, coupling the maintenance and rescue Digihaler™ will allow the collection of a significant amount of information both about baseline therapies and exacerbations. Furthermore, the granular data collected from these inhalers will be invaluable in determining the impact of inhalation parameters on predicting asthma outcomes and in determining whether these measurements can serve as surrogates of expiratory flow measurements that are the cornerstone of asthma management but often challenging to obtain in real world settings. Coupling digital biomarkers from the inhaler with biological and clinical characteristics in a cohort of severe asthma patients will lead to an enhanced ability to not only understand the impact of

maintenance therapies on asthma outcomes but will also provide us with the opportunity to use machine learning algorithms to develop predictive models that may enhance our ability to predict response to biologics.

Precision medicine approaches to severe asthma are in their infancy and the application of complex techniques to help guide therapy are urgently needed. Currently, patients that are partial responders or non-responders to given therapies are switched between available biologics, and clinical response is assessed 4-6 months after the new therapy is initiated. This represents an inefficient approach that is both time consuming and costly to patients and payers.

We propose that variability in patterns of inhaler use, inhalation parameters, and overall medication adherence will significantly impact response to biologics in patients with severe asthma. Furthermore, the additive impact of predictive biomarkers, digital markers, and clinical characteristics will allow the development of a predictive algorithm that will help identify responders and enhance our understanding of the heterogeneous responses to therapy.

